- t. Stool sample will be collected at each time point indicated. For the visit that endoscopy will be conducted, stool sample should be collected prior to endoscopy. If a sample cannot be obtained during the site visit, the site will give instructions and a stool sample supply kit (supplies will be provided at the time-points indicated). All stool samples should be collected before any bowel preparation for endoscopy is started and should be returned to the site within 3 days of collection. Stool sample supply kit to be provided at Week 8 visit for subjects entering into the extended treatment program.
- u. Reference Section 5.3.2.1 regarding PK sample collection procedures. The Week 8 PK sample will be the Baseline PK sample for Substudy 3. PK should only be collected at the Premature discontinuation visit if the subject discontinues before the Week 8 visit, it is not relevant for subjects discontinuing during Substudy 2 Part 2.
- v. Blood samples will be collected at the visits indicated and will be utilized to assess effects of upadacitinib inhibition on certain lymphocyte subsets, including T (CD4+ and CD8+) cells, B (CD19+) cells, natural killer (NK) cells, and natural killer-T (NKT) cells.
- w. IBDQ = Inflammatory Bowel Disease Questionnaire; SF-36 = Short-Form 36; EQ-5D-5L = European Quality of Life 5 Dimensions 5 Levels; WPAI = Work Productivity and Activity Impairment; FACIT F = Functional Assessment of Chronic Illness Therapy – Fatigue; PGIC = Patient Global Impression of Change. PGIC will not be collected at Baseline; UC-SQ = UC Symptoms Questionnaire. PGIS = Patient Global Impression of Severity will only be collected from subjects in Substudy 2 (Parts 1 and 2) and only at select sites.
- x. Collection of Serious Adverse Events (SAEs) begins the day the subject signs the informed consent. During each study visit subjects will also be asked to report UC related Health Care Resource Utilization (Unscheduled Outpatient Visits, Emergency Room Visits and Hospitalizations and surgeries) and will be captured as a part of supplemental healthcare resource utilization (HCRU) form of AE collection in EDC.

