For ITT_A population, additional efficacy endpoints will be analyzed by comparing each upadacitinib treatment group and placebo group. The binary endpoints and change from baseline continuous endpoints will be analyzed by CMH and RTB-MI with MMRM/ANCOVA, respectively, and the corresponding analyses are specified in Section 8.3. Change from maintenance baseline continuous endpoints will be analyzed by ANCOVA. The NRI-C approach will be used for missing data handling in the analyses of binary efficacy endpoints. For incidence rate of UC-related hospitalization and surgery during the Maintenance Study, adjusted incidence rates will be used to compare the risk between each upadacitinib treatment group and placebo group. Adjusted rates will be calculated as the number of subjects with the respective event divided by the time at risk. For subjects with an event during the Maintenance Study, time at risk is the patient-years (PYs) from Week 0 to the first event. For subjects without event, time at risk is PYs from Week 0 to the end of 30-day follow up period. Relative risk ratios of the incidence rates and confidence intervals will be calculated to evaluate the statistical significance of the difference between each upadacitinib treatment group and placebo group using z-score normal approximations. For multi-level categorical endpoints PGIC and PGIS, percentage of each outcome category will be reported descriptively, and no statistical comparison will be performed.

For ITT_B, ITT_C and ITT_E populations, the primary and secondary endpoints (specified in Section 3.1 and Section 3.2) will be summarized and descriptive statistics will be provided. The approaches of NRI-C and RTB-MI with MMRM/ANCOVA will be used for missing data handling in the analyses of binary and continuous efficacy endpoints, respectively.

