3.0	10 May 2021	
 • Removed incidence rate of UC-related hospitalization and surgeries through Week 52 from secondary endpoints in Section 3.2, and add both as additional efficacy endpoints in Section 3.3 • Updated additional endpoints in Section 3.3: added clinical remission per Partial Mayo score and corticosteroid free over time among subjects taking corticosteroid at Baseline in the Induction Study, changed the evaluation of SFS and RBS from Week 40 and 48 to Week 36 and Week 44 in endpoint achievement of $SFS \leq 1$ (and not worse than Baseline), $RBS = 1$ at both Week 36 and Week 44, clinical remission per Adapted Mayo score at Week 52 and corticosteroid free for ≥ 90 days immediately preceding Week 52 among subjects taking corticosteroids at Baseline in the Induction Study. • Clarified the definition of ITT populations and scopes of analyses in data base lock for each ITT population in Section 4.0. • Clarified the subject disposition and compliance summary in Section 5.0 and Section 6.0, respectively • Specified the derivation of confidence interval for difference in proportions between treatment groups using NRI-C approach in Section 8.3.1 in response to a comment from FDA on December 10, 2020. • Updated the potential intercurrent events in Section 8.2 • Added DAMI as a sensitivity analysis for continuous key secondary endpoints to assess the impact of potential departures from the MAR assumption in Section 8.4 • Clarified the analysis method of multi-level categorical endpoints PGIC and PGIS in Section 8.6. The two endpoints will be reported only descriptively using AO approach. Consequently, the random seeds of NRI-C for PGIC and PGIS has been removed from Table D-1. • Added Baseline aminosalicylate use (yes, no) as a subgroup analysis. • Clarified the baseline for safety analysis in Section 9.1. • Added risk difference and 95% CI for TEAE analysis of SA_A and SA_D populations in Section 9.2. • Clarified the interim analysis in Section 11.0. • Updated the type-I error control approach in Section 12.0

Table 3. SAP Version History Summary (Continued)

Version	Date	Summary

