3.3 Other Efficacy Endpoints

The following additional efficacy endpoints will be evaluated for Part 1:

- The achievement of response in IBDQ Bowel Symptom domain (defined as increase of IBDQ bowel symptom domain score ≥ 6 from Baseline) at Week 8;
- The achievement of response in IBDQ fatigue item (defined as increase of IBDQ fatigue item score ≥ 1 from Baseline) at Week 8;
- The achievement of SFS of 0, RBS of 0 and endoscopic subscore of 0 at Week 8;
- The achievement of SFS of 0, RBS of 0 and endoscopic subscore of ≤ 1 at Week 8;
- The achievement of clinical remission per Full Mayo score at Week 8;
- Change in Full Mayo score from Baseline at Week 8;
- The achievement of clinical remission per Partial Mayo score over time;
- The achievement of clinical response per Partial Adapted Mayo score over time;
- The achievement of clinical response per Partial Mayo score over time;
- The achievement of SFS ≤ 1 over time;
- The achievement of RBS of 0 over time;

- The achievement of Fecal calprotectin below 150 mg/kg over time;
- Change from Baseline in fecal calprotectin over time;
- Change from Baseline in hs-CRP over time;
- Change from Baseline in Partial Adapted Mayo score, Partial Mayo score and SFS, RBS over time;
- Change from Baseline in UCEIS score over time;
- Change from Baseline in laboratory and nutritional parameters (e.g., hemoglobin, hematocrit, albumin, total protein concentration, and weight);
- Change from Baseline in subject-reported stool frequency (absolute values) over time;
- Change from Baseline in IBDQ total and domain score over time;
- Change from Baseline in individual IBDQ item under Bowel Symptom domain (for Q1, Q5, Q9, Q13, Q17, Q20, Q22, Q24, Q26, and Q29) over time;
- The achievement of IBDQ response (defined as increase of IBDQ total score ≥ 16 from Baseline) over time;
- The achievement of IBDQ remission (defined as IBDQ total score ≥ 170) over time;
- Change from Baseline in EQ-5D-5L score over time;
- Change from Baseline in WPAI scores over time;
- Change from Baseline in SF-36 Physical Component Summary (PCS) and Mental Component Summary (MCS) components and domain scores over time;
- Summary of PGIC improvement category over time;
- Summary of PGIS severity category over time;
- Change from Baseline in FACIT-F score over time;
- Change from Baseline in UC-SQ score over time;
- UC-related hospitalizations through Week 8;
- UC-related surgeries through Week 8;
- All-cause hospitalizations through Week 8;

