8.3.1 Categorical Endpoints

[figure not shown]
[figure not shown]
For binary efficacy endpoints, missing data will be handled using the following approaches:

- The primary approach for handling missing data in the analysis of binary endpoints will use **Non-Responder Imputation** while incorporating Multiple Imputation (MI) to handle missing data due to **CCOVID-19 (NRI-C)**.

The NRI-C will categorize any subject who does not have an evaluation during a pre-specified visit window (either due to missing assessment or due to early withdrawal from the study) as a non-responder for the visit. The only exception is that missing data due to COVID-19 infection or logistical restrictions related to the COVID-19 pandemic will be handled by Multiple Imputation (MI). At each visit, subjects will be characterized as responders or non-responders based on MI imputed values if missing due to COVID-19; otherwise, subjects will be considered as non-responders for missing due to other reasons in the NRI-C approach. In addition, at or after the occurrence of the UC-related corticosteroids intercurrent event (see Section 8.2), subjects will be counted as non-responders.

- A sensitivity analysis for categorical endpoints will use **NR**I**** with **No** special data handling for missing due to **CCOVID-19 (NRI-NC)**.

NRI-NC will be performed in the same way as NRI-C without the exception above. Missing due to COVID-19 infection or logistical restrictions will also be counted as non-responders. Subjects at or after the occurrence of the UC-related corticosteroids intercurrent event will still be counted as non-responders. This is the same method as the "NRI" defined in the protocol.

-
- Hybrid Multiple Imputation Method (HMI): Sensitivity analysis will be performed using hybrid multiple imputation method for the primary endpoint. Subjects who discontinue study drug prior to Week 8 due to lack of efficacy or AEs and have no available measurements will be considered as "non-responder" for clinical remission. Subjects who discontinue for other reasons and have no available measurements will be categorized according to the data from multiple imputations.

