8.6 Additional Efficacy Analyses

Additional efficacy endpoints are defined in Section 3.3. The estimands corresponding to the additional efficacy endpoints are defined for each of the binary additional endpoints as follows: difference in the percentage of subjects achieving binary endpoints; regardless of premature discontinuation of study drug and without initiation or dose escalation of UC-related corticosteroids (See Section 8.2.2) in the upadacitinib 45 mg QD and placebo groups in the ITT population. The estimands corresponding to the additional efficacy endpoints are defined for each of the continuous additional endpoints as follows: difference in the mean change from baseline regardless of premature discontinuation of study drug and if subjects would not initiate or escalate dose of UC-related corticosteroids

(See Section 8.2.2) in the upadacitinib 45 mg QD and placebo groups in the ITT population. For ITT1 Population, additional efficacy endpoints in Part 1 will be analyzed by comparing upadacitinib treatment group and placebo group. The categorical endpoints and continuous endpoints will be analyzed by CMH and MMRM (or ANCOVA), respectively, and the corresponding analyses are specified in Section 8.2. The NRI-C approach will be used for missing data handling in the analyses of categorical efficacy endpoints.

For ITT2 population, descriptive statistics will be provided for additional efficacy endpoints in Part 2. The NRI-C approach will be used for missing data handling in the analyses of categorical efficacy endpoints.

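### Substudy 2 SAP 8.6 and Table D-1 apply NRI-C to the seven-level PGIC and PGIS, for which no responder is defined; for PGIS the rule also scores non-collection by design as non-response

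*SAP*

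**What the plan says.** **Endpoints.** Substudy 2 SAP 3.3 lists both instruments for Part 1 as category summaries: "Summary of PGIC improvement category over time" and "Summary of PGIS severity category over time". Protocol Appendix G gives each of them seven response options. Neither document sets a cut that would make a subject a responder.

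**Analysis.** Substudy 2 SAP 8.6 says of the additional endpoints in ITT1: "The categorical endpoints and continuous endpoints will be analyzed by CMH and MMRM (or ANCOVA), respectively". It then adds: "The NRI-C approach will be used for missing data handling in the analyses of categorical efficacy endpoints". PGIC and PGIS are not excepted. Table D-1 in Appendix D, which holds the NRI-C seeds, has a row for each of them on a 0 to 6 scale (PGIC 21491 and 22071; PGIS 21492 and 22072).

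**The rule.** Section 8.3.1 introduces its methods as applying to binary endpoints. It then says: "The NRI-C will categorize any subject who does not have an evaluation during a pre-specified visit window", and the category is non-responder. The only exception is missingness due to COVID-19, which goes to multiple imputation.

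**Collection.** Protocol Appendix C, footnote w, says that PGIS "will only be collected from subjects in Substudy 2 (Parts 1 and 2) and only at select sites". Section 4.0 of the Substudy 2 SAP uses ITT1 for all Part 1 efficacy analyses and defines no subset of PGIS sites.

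**The other SAP.** Substudy 3 SAP 8.6 says: "For multi-level categorical endpoints PGIC and PGIS, percentage of each outcome category will be reported descriptively, and no statistical comparison will be performed". Its version 3.0 log adds: "The two endpoints will be reported only descriptively using AO approach", and records that the NRI-C seeds for both were removed.

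**The concern.** NRI-C needs a yes/no outcome. On a seven-level scale with no cut it gives no answer, so a programmer would have to invent one: a dichotomy, a default category, or an extra missing category in the denominator. These choices give different tables, and the plan does not choose between them.

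For PGIS the question is also who belongs in the denominator. A subject at a site without the questionnaire has no PGIS value because none was planned. NRI-C does not separate that subject from one who dropped out. Read literally, the reported PGIS percentages would depend partly on how many sites carried the instrument.

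At stake are the readability and size of two descriptive results, and consistency with how Substudy 3 presents the same instruments.

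**Working it through.** **1. Figures in the plan.** The documents give no rate, sample size or power for PGIC or PGIS. The one related figure is the primary-endpoint power in Substudy 2 SAP 2.4: above 95% for 5% versus 18% with 154 and 308 subjects. It reproduces (98.8% by the pooled normal approximation, 98.9% by exact Fisher) and is untouched by this point. Only the arm sizes are used below.

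**2. Does the rule yield a value?**

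| Needed for NRI-C | PGIC | PGIS |
|---|---|---|
| Binary outcome (8.3.1) | No, seven levels | No, seven levels |
| Responder definition (3.0, 3.3) | None | None |
| Estimand in 8.6 (binary or continuous only) | Neither fits | Neither fits |
| Named as an NRI-C endpoint (Table D-1) | Yes | Yes |

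The rule is assigned to both scales but defined for neither.

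**3. PGIS denominator.** Let s be the share of ITT1 at PGIS sites, taken as about equal in the two arms. Let p_T and p_C be the true shares in a favourable category. Ignore other missingness and the COVID-19 exception.

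- Favourable category or favourable-category responder on full ITT1: the rate becomes s × p, and the difference becomes s × (p_T − p_C).
- Missing coded to the worst category, whose true share is w: that category becomes s × w + (1 − s), which is at least 1 − s.

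**4. Illustration.** The rates (45% upadacitinib, 20% placebo) and s are assumptions; neither is in the documents.

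| s | Upadacitinib | Placebo | Difference |
|---|---|---|---|
| 100% | 45.0% | 20.0% | 25.0 points |
| 75% | 33.8% | 15.0% | 18.8 points |
| 50% | 22.5% | 10.0% | 12.5 points |
| 25% | 11.3% | 5.0% | 6.3 points |

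As a check at s = 50%, 154 of 308 and 77 of 154 subjects have PGIS. Then 0.45 × 154 = 69.3 and 69.3/308 = 22.5%; 0.20 × 77 = 15.4 and 15.4/154 = 10.0%. Limiting the denominator to PGIS sites restores 25 points. Under worst-category coding at s = 50%, at least half of each arm would appear in the worst category, whatever w is.

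**5. Effect on a nominal test of that dichotomy.** At s = 50%, power is 93% on full ITT1 against 97% at PGIS sites only. At s = 25% it is 61% against 77%.

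**The case against.** The strongest reply is that the plan never meant this. Section 8.3.1 limits itself to binary endpoints, 3.3 uses summary wording for these two where its binary endpoints are worded as achievements, and the protocol likewise lists proportions by category. The seeds in Table D-1 serve only the COVID-19 imputation step, so they do not show that uncollected PGIS values are to be scored as failures. On this view a plain category table was always intended. The Substudy 3 log calls its own change a clarification, and it is dated 10 May 2021, after the Substudy 2 SAP (version 5.0, 13 November 2020).

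That stands as evidence of likely intent, and the Substudy 3 change cannot be cited as proof of an error in Substudy 2. It does not settle the text. Section 8.6 extends NRI-C from binary to categorical endpoints without exception, and Table D-1 names both scales. The SAP contradicts itself, and the more specific statements point to NRI-C.

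Other parts of the reply also stand:

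- A reader might infer that CMH is wrong for seven ordered levels. It is not in itself; CMH methods cover multi-category outcomes. The defect lies in NRI-C and the missing definition.
- A reader might infer that PGIC is diluted too. Appendix C and Protocol 5.3.1.1 attach the site limit to PGIS only. The synopsis sentence naming both instruments is ambiguous and is not enough to extend it.
- A reader might infer that site selection could create or reverse a treatment effect. Randomisation is central and so s should be similar in both arms; the effect is attenuation.

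**Conclusion.** The point holds as a specification defect with limited reach. NRI-C is assigned to PGIC and PGIS without an outcome on which it can act. For PGIS, its literal text also treats absence by design as non-response on the full ITT1 denominator.

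A reader might go further and conclude that every subject at the other sites becomes a failure and that the reported PGIS results will certainly shrink. The documents do not support that. Shrinkage by s follows only if category percentages are taken on all of ITT1 or a favourable-category responder is used. Worst-category coding raises that category's share instead. Missingness due to COVID-19 is imputed, not failed. Because s and any cut are absent from the documents, the actual size cannot be computed; the 12.5 points at s = 50% rests on an assumed 25-point difference and equal s in the arms.

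The primary and ranked secondary endpoints are untouched. Under Substudy 2 SAP 12.0 the additional endpoints are tested at nominal alpha without multiplicity adjustment, and neither scale is in the Part 2 list. This is a desirable clarification and does not threaten the trial's conclusions.

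**What to change.** In Substudy 2 SAP 8.6, exempt PGIC and PGIS from NRI-C and from the between-group test. Report the percentage in each category descriptively and as observed. This agrees with Substudy 3 SAP 8.6, which makes the presentation descriptive, and with its version 3.0 log, which supplies the as-observed handling.

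State that the PGIS denominator is subjects with a PGIS value at sites that collect it, and show that number by arm. This is an addition, since the Substudy 3 SAP does not write it down either. Delete the PGIC and PGIS rows from Table D-1.

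The documents do not give the Substudy 2 lock date. If the database is already locked, record the change in an addendum or the study report.

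The cost is a sentence or two and two table rows. The downside is that no nominal p-value is produced for these two endpoints. If one is wanted, the SAP would instead have to define a responder and a PGIS-site analysis set.

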8.7 Efficacy Subgroup Analyses

The following subgroup analyses will be conducted for the primary efficacy endpoint in the ITT1 population. Treatment difference between upadacitinib treatment group and placebo group with point estimate and 95% confidence interval using normal approximation will be presented. The NRI-C approach will be used for missing data handling. No p-value will be provided for subgroup analysis.

- Sex (male, female)
- Age (\leq median, $>$ median)
- Race (white, non-white)
- Bio-IR status (Bio-IR, non-Bio-IR)
- Baseline corticosteroid use (yes, no)
- Baseline Adapted Mayo score (≤ 7 , > 7)
- Baseline Full Mayo score (≤ 9 , > 9)
- Prior exposure to anti-TNF (yes, no) for non-Bio-IR
- Prior exposure to biologic therapy (yes, no) for non-Bio-IR
- Baseline weight (\leq median, $>$ median)
- Presence of pancolitis at Baseline (yes, no)
- Disease duration at Baseline (\leq median, $>$ median)

- Baseline hs-CRP (≤ 5 mg/L and > 5 mg/L)
- Region (US versus non-US)

In addition, the following key secondary efficacy endpoints will be analyzed in the Bio-IR and non-Bio-IR subgroups in the ITT1 population.

- Endoscopic remission at Week 8
- Endoscopic improvement at Week 8
- Clinical response per adapted Mayo score at Week 8

9.0 Safety Analyses

9.1 General Considerations

Safety analyses will be performed on the safety populations in the 8-week DB induction period (Part 1, SA1 population) and the 8-week OL extended treatment period (Part 2, SA2 population). In addition, safety summaries will be provided on the all upadacitinib treated safety population (SA-UPA).

The standard safety analyses will include reporting of adverse events (AEs), adverse events of special interest (AESIs), laboratory, and vital signs measurements. Frequency tables and exposure adjusted event rate per 100 patient-years tables of subjects with treatment-emergent adverse events (TEAEs) by system organ class (SOC) and by preferred term (PT) as in the Medical Dictionary for Regulatory Activities (MedDRA) dictionary will be provided by treatment group. All continuous laboratory parameters and vital signs variables at each visit will also be summarized by treatment group. Frequency tables of subjects meeting criteria for potentially clinically important vital sign values and for potentially clinically important laboratory values will be provided by treatment group.

The Baseline for safety analysis will be treatment dependent. For SA1 population, laboratory and vital signs measurements, the Baseline value is defined as the last available measurement before study drug administration for each subject. For SA2 and SA-UPA

populations, the Baseline value is defined as the last available measurement before first dose of upadacitinib.

Missing safety data will not be imputed.

9.2 Adverse Events

Adverse events (AEs) will be summarized and presented using primary MedDRA System Organ Classes (SOCs) and preferred terms (PTs) according to the version of the MedDRA coding dictionary used for the study at the time of database lock. The actual version of the MedDRA coding dictionary used will be noted in the AE tables and in the clinical study report. Specific adverse events will be counted once for each subject for calculating percentages, unless stated otherwise. In addition, if the same adverse event occurs multiple times within a subject, the highest severity and level of relationship to investigational product will be reported.

